Econometric analyses for Aim 3. Using DID methods, we will calculate the average pre-post difference in total Medicaid expenditures attributable to the subpopulation of newly insured patients in Oregon OCHIN CHCs, subtracted by the average difference among the already insured patients. We will assess changes in spending immediately after Medicaid expansion in Oregon clinics as well as comparing subsequent years post-expansion. Specifically, we will first assess the initial increase in Medicaid expenditure after the expansion (post t_1). In this case, because newly insured were uninsured at the pre-period, thus incurring no cost to Medicaid, their cost will be equal to \$0. Next, we will assess the change between post at t_1 (i.e., 2014) versus post at t_2 (i.e., 2015) versus post at t_3 (i.e., 2016) to evaluate whether the initial cost-increase is reduced overtime and by how much. Changes in spending after Medicaid expansion among newly insured vs. spending changes in already insured will 'net out' any secular changes not related to Medicaid expansion. Any remaining significant differences in outcome – DID – are attributed to Medicaid expansion. These findings will help to assess whether Medicaid expansion can help reduce costs, and if so, whether the reduction comes from lowering the spending associated with unnecessary or inefficient use of services external to CHCs. We note that CHCs do not have incentives to act as gatekeepers to this care. Therefore, reductions in spending for these external services would most likely reflect improvements in care delivery within CHCs. Analytically, the DID estimate is represented by the marginal effect on the interaction between a dummy variable indicating that the observations occur in the post-Medicaid expansion period and a dummy variable indicating newly insured individuals. We will also include patient-level variables to account for predisposing factors and need for services, as identified by the Aday and Andersen model. A variety of factors must be addressed in our DID estimation: *Accounting for clinic-level effects.* Our study will focus on the 'treatment-effect' of the Oregon Medicaid expansion: How does expanding Medicaid affect healthcare spending? Since this is our main focus, our approach is to use clinic-level fixed effects to net out any time-invariant differences in clinic-level outcomes. However, recognizing the potential interest in clinic-level effects, in secondary analyses we will test hierarchical (mixed) models to more

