For **Aim 1**, the primary dependent variables are insurance coverage, utilization of services, and receipt of preventive services in the pre- and post-expansion periods, in expansions versus non-expansion states. To assess service utilization, we will ask questions such as: Has the overall number of CHC services (e.g., visits, immunizations, referrals) increased? To assess preventive services, we will use clinical quality metrics for process (e.g., blood pressure screening rates in the clinic). The primary independent variable is whether a CHC is in a state that expanded Medicaid or not. For **Aim 2**, the primary dependent variables are utilization of services and receipt of preventive services among cohorts of individual patients in expansion states. To assess service utilization, we will ask questions such as: Has the number of primary care visits, per patient, increased? To assess preventive services, we will use clinical quality metrics for process (e.g., breast cancer screening rates among patient cohorts). The primary independent variable is whether a patient is newly insured, already insured, or uninsured. For **Aim 3**, the primary dependent variables are utilization of services in CHCs and external to CHCs and Medicaid expenditures in Oregon. To assess service utilization, we will ask questions such as: What is the rate of hospitalizations in newly versus already insured patients? To assess Medicaid expenditures, we will ask: Are there differences in Medicaid expenditures between newly insured versus already insured patients? Do expenditures plateau over time for newly insured patients? The primary independent variable is whether an Oregon patient is newly insured or already insured. Other covariates for patient- and clinic-level analyses in the three aims include predisposing factors and need for services as described in Box 6, above.

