We examined differences in utilization among patients newly gaining Medicaid coverage (*newly insured*), as compared to utilization among individuals who are already insured by Medicaid (*already insured*) and those who remain uninsured (*uninsured*). Additionally, in subpopulation analyses restricted to the state of Oregon (an expansion state), we link EHR data from Oregon CHC clinics to Oregon’s Medicaid administrative claims data to investigate post-expansion overall healthcare utilization and Medicaid expenditures among the newly insured as compared to the already insured. Inclusion and exclusion criteria were modified for some analyses; see below for details on specific paper analyses.

Table 2. Study population stratified by expansion status and state

2014 Expansion status	State	N facilities	N patients
Expansion	California	48	163,686
Expansion	Hawaii	2	10,075
Expansion	Maryland	24	15,297
Expansion	Minnesota	4	12,725
Expansion	New Mexico	25	63,488
Expansion	Nevada	3	2,326
Expansion	Ohio	15	55,537
Expansion	Oregon	121	261,166
Expansion	Rhode Island	59	38,946
Expansion	Washington	6	24,585
Non-expansion	Alaska*	1	3,820
Non-expansion	Florida	169	412,138
Non-expansion	Indiana**	10	16,200
Non-expansion	Kansas	9	8,047
Non-expansion	Missouri	3	16,461
Non-expansion	Montana	6	13,155
Non-expansion	North Carolina	21	39,726
Non-expansion	Texas	5	11,383
Non-expansion	Wisconsin***	8	20,593

*Alaska expanded Medicaid to 138% FPL on 9/1/2015 and was excluded from some analyses; **Indiana expanded Medicaid to 138% FPL on 2/1/2015 and was excluded from some analyses; ***Wisconsin expanded Medicaid from 0% to 100% on 1/1/2014 and therefore more closely resembled an ACA expansion state.

Wisconsin was considered an expansion state in analyses.

Stakeholder Engagement

The project team engaged a Patient Investigator ([name]) and a Clinician Investigator ([name], MD) throughout the duration of the project. These stakeholders advised the project team during the data analysis, manuscript development, and dissemination phases of the project. Their involvement was facilitated through ongoing training about the research process, collaboration with research team about data analyses challenges, data interpretation,

and manuscript development, and dissemination of research aims through presentations and blogging.

Data Analyses

Medicaid Expansion Produces Long-Term Impact on Insurance Coverage Rates in Community Health Centers

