Full Citation	[name], N., Hoopes, M. J., Angier, H., Marino, M., Holderness, H., & DeVoe, J. E. (2017) Medicaid Expansion Produces Long-Term Impact on Insurance Coverage Rates in Community Health Centers. J Prim Care Community Health. 8(4):206-212.
Objective	Assess change in insurance coverage rates pre- and post-ACA in Medicaid expansion and non-expansion states for community health center patients.
Study Population	N=875,571 patients; Inclusion: ages 19-64 with ≥ 1 visit between 2012 and 2015. Setting: 412 primary care CHCs in 9 expansion and 4 non-expansion states.
Exclusion Criteria	Pregnant women
Independent Variables	Whether state had taken Medicaid expansion as of January 1, 2014.
Dependent Variables	Health care delivery: rates of billed encounters (all, primary care, new patient, established patient), receipt of preventive services (preventive medicine visits, immunizations, medications ordered). 1. Insurance type: uninsured, Medicaid-insured, privately-insured.
Covariates	Clinic-level: distributions of sex, age, race/ethnicity, primary language, federal poverty level. State-level: marketplace type, 2013 minimum wage, 2013 uninsured rate, 2013 unemployment rate.
Analysis Plan	Post- versus pre-expansion rate ratios within expansion group; difference-in-difference ratios (comparing post- versus pre-period changes between expansion states vs non-expansion states); and second year post- (2015) versus first year post-ACA (2014) rate ratios within expansion group.
Data Set Name	OCHIN: e:\sasroot\PPDA\P_Huguet_24mo
Code Location	OCHIN SAS server

Oregon Medicaid Expenditures After the 2014 Affordable Care Act Medicaid Expansion: Over-time Differences Among New, Returning, and Continuously Insured Enrollees

Full Citation	Springer, R., Marino, M., O'Malley, J. P., Lindner, S., [name], N., & DeVoe, J. E. (2018). Oregon Medicaid Expenditures After the 2014 Affordable Care Act Medicaid Expansion: Over-time Differences Among New, Returning, and Continuously Insured Enrollees. Med Care, 56(5) , 394-402.
Objective	To assess health care expenditures among Medicaid enrollees in the 24 months after Oregon's 2014 Medicaid expansions and examine whether expenditure patterns were different among the newly, returning, and continuously insured.
Study Population	Oregon adult Medicaid beneficiaries insured continuously from 2014 to 2015 who were either newly, returning, or continuously insured.

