Exclusion Criteria	Our study population included adults aged 19-64 insured by Oregon Medicaid continuously from January 2014 through December 2015. We excluded patients without coverage on 1/1/2014 and those with coverage gaps during the study period. We excluded patients with dual Medicaid and Medicare eligibility and whose 2014-2015 eligibility did not depend on FPL (e.g. pregnant women). Of 622,513 adults aged 19-64 with any 2014 Medicaid enrollment, 230,602 (37%) remained in our sample.
Independent Variables	Insurance group, time, and their interaction terms, mean monthly expenditures.
Dependent Variables	standardized expenditures for inpatient care, prescription drugs, and total outpatient care in addition to subdivisions of outpatient: outpatient claims were classified as either emergency department, dental, mental and behavioral health, primary care evaluation, management, and procedures, specialist evaluation, management, and procedures, and primary care/specialist imaging or tests based on a hierarchical system involving procedure code, provider type, provider specialty, place of service, and associated costs.
Covariates	The patient's age, sex, racial and ethnic background, rural setting, and comorbidity level as assessed by the enhanced Charlson comorbidity index score.
Analysis Plan	Retrospective cohort study using inverse-propensity weights to adjust for differences between groups. We summarized enrollee

	utilization outcomes as mean monthly expenditures, running a separate (two-part) hurdle model for each type.
Data Set Name	NPAT, INPATIENT_Q42015, OUTPAT, OUTPATIENT_2015Q4, RX , RX_Q42015, SAMPLE, SAMPLE_with_weights FY_2015_FR_AND_CN_Table 5, Nov 2013 Fee Schedule – Excel, January 2014 Behavioral Health Fee Schedule, January 2014 Mental Health Fee Schedule – Excel
Code Location	Box at OHSU

Medicaid Coverage Accuracy in Electronic Health Records

Full Citation	Marino, M., H. Angier, S. Valenzuela, M. Hoopes, M. Killerby, B. E. Blackburn, N. [name], J. [name], B. Hatch, J. P. O' Malley and J. E. DeVoe (2018). Medicaid Coverage Accuracy in Electronic Health Records . Prev Med Reports 11 : 297–304.
Objective	To evaluate the validity of EHR data for monitoring longitudinal Medicaid coverage and assess variation by patient demographics, visit types, and clinic characteristics.

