Additionally, we will partner with the state cancer registries of one or more states to complete probabilistic linkage between our patient population and reported cancer cases. It is currently unknown how well personal cancer history and related data are documented in the outpatient EHR (i.e., data contained in the ADVANCE CDRN), thus our ability to identify and characterize cancer survivors may be incomplete. A linkage with one or more state cancer registries will supplement the CDRN data by comprehensively identifying cancer survivors in our cohort. This will allow us to test and validate our EHR-based algorithms, and to evaluate post-cancer care services provided by community health centers and the impact of insurance coverage for this population.

5) Study Population

a) Number of Subjects

Approximately 2.3 million total possible subjects. All analyses will contain a subset of these subjects.

b) Vulnerable Populations

Children ages 0-18 will be included for methods development and analyses related to childhood cancer and long-term care for cancer survivors. There is little literature about childhood cancers in vulnerable populations (e.g., economically marginalized, uninsured, or Medicaid insured) and associated disparities. Furthermore, adults with a history of childhood or adolescent cancer may require special follow-up care and screening

throughout their adult lives, thus we wish to have access to their EHR records from earlier ages where available.

c) Setting

This research will be conducted in collaboration with OCHIN. OCHIN requests the OHSU IRB serve as the IRB of record for this study.

d) Recruitment Methods and Consent Process

All patients with data in the ADVANCE CDRN may be included in this study. Subsets may include only OCHIN EHR data, only Oregon OCHIN EHR data, only persons with certain diseases or conditions (*e.g.*, cancer, diabetes, obesity), etc. For analysis of expenditures, Oregon OCHIN clinics from the ADVANCE CDRN will be linked to Oregon Medicaid administrative data using Medicaid identification number; subjects found in both datasets will be included. Similarly, for cancer registry linkage analyses only patients identified in both datasets will be included in analyses.

The ADVANCE data was collected under a waiver of authorization as the data warehouse poses very little risk to patients, and it was not practical to consent the number of patients included in the dataset.

6) Procedures

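### The only expenditure analysis under Data Analyses uses a statewide cohort of continuously enrolled Medicaid adults, so as described it does not estimate Aim 3's contrast among Oregon CHC patients

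*Combined protocol and SAP*

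**What the plan says.** **Planned population.** The SAP (B.4.4, Econometric analyses for Aim 3) sets the target as the pre-post change in "total Medicaid expenditures attributable to the subpopulation of newly insured patients in Oregon OCHIN CHCs", minus the corresponding change among the already insured. For the main model, "our approach is to use clinic-level fixed effects to net out any time-invariant differences in clinic-level outcomes". In the SAP's list of outcomes for Aim 3, "the primary dependent variables are utilization of services in CHCs and external to CHCs and Medicaid expenditures in Oregon".

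The combined document agrees with this in three places:
- Data Sources says that Oregon Medicaid data were linked to the OCHIN Oregon clinics to capture outside services and spending.
- Study Population and Study Period says of the Oregon subpopulation analyses that "we link EHR data from Oregon CHC clinics to" the state's Medicaid claims.
- The IRB protocol, section 5d, says of the expenditure analysis that "subjects found in both datasets will be included".

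**Listed analysis.** Under Data Analyses, the entry on Oregon Medicaid expenditures after the 2014 expansion gives its population as "Oregon adult Medicaid beneficiaries insured continuously from 2014 to 2015", divided into newly, returning and continuously insured. The exclusions row reports: "Of 622,513 adults aged 19-64 with any 2014 Medicaid enrollment, 230,602 (37%) remained in our sample". People also eligible for Medicare, and people whose eligibility was not tied to the poverty level, were removed. The covariates are age, sex, race and ethnicity, rural setting and comorbidity. The model is an inverse-propensity-weighted two-part hurdle model, fitted separately for each type of spending. The named files are inpatient, outpatient, pharmacy, sample and fee-schedule files.

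**The concern.** The population in the entry is not the one that the SAP and the protocol describe. Three things that Aim 3 needs are not stated: a rule that ties a person to a CHC, a clinic term in the model, and a division of spending into CHC and external services. Outpatient spending is divided by type of service instead.

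This matters because of how the SAP intends to read the result. It argues that a fall in spending on services outside CHCs would most likely reflect better care delivery inside them. That argument needs patients who use CHCs, and spending separated by where it arose. A pooled statewide estimate could differ from the CHC-patient estimate in either direction, and nothing in the entry lets a reader check.

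**Working it through.** **Step 1. Reproduce the plan's own figure.** 230,602 / 622,513 = 0.370, which agrees with the stated 37%. The number excluded is 622,513 − 230,602 = 391,911.

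**Step 2. Set the texts side by side.**

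| Element | SAP and protocol | Expenditure entry |
|---|---|---|
| Who | Patients of Oregon OCHIN CHCs | Oregon Medicaid adults with continuous 2014–2015 coverage |
| Data | EHR linked to Medicaid claims | Named files are claims, sample and fee-schedule files |
| Clinic adjustment | Clinic fixed effects | None stated |
| Place of service | Inside versus outside CHCs | By type of service |

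The neighboring entry on the accuracy of Medicaid coverage in the EHR does state CHC visits and the link to state records (135,514 patients, 184 Oregon CHCs). So these entries do record a CHC restriction when there is one.

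**Step 3. Compare the starting frame with the study's Oregon CHC patients.** Table 2 gives 261,166 Oregon patients, of any payer, at 121 facilities. Even if every one of them were in the frame:
- largest possible share of the frame: 261,166 / 622,513 = 42.0%
- smallest possible number outside Table 2: 622,513 − 261,166 = 361,347, or 58.0%

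**Step 4. Ask whether this carries over to the analyzed sample.** It does not. Because 261,166 is larger than 230,602, Table 2 puts no limit on the CHC share of the final sample. The final sample exceeds the SAP's Aim 3 sample size by 230,602 − 187,684 = 42,918, but 187,684 is a planning figure from a preliminary data pull, not a count of all Oregon CHC Medicaid patients.

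**Step 5. Size of a linked-CHC analysis.** The documents do not give it. Assume that the 37.04% retention also held among CHC patients. Then n = 0.3704 × N. With equal variance, and ignoring clustering and weighting, intervals widen by √(230,602 / n).

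| Starting count N | n | Interval width ratio |
|---|---|---|
| 135,514 (linked validation cohort) | about 50,200 | 2.14 |
| 187,684 (SAP Aim 3) | about 69,500 | 1.82 |
| 261,166 (Table 2, includes non-Medicaid patients) | about 96,700 | 1.54 |

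Limiting the cohort to patients seen before 2014 would reduce these numbers further.

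**The case against.** The strongest defense is that the document discloses the change where it says it will. Study Population and Study Period warns that criteria were altered for some analyses and sends the reader to the individual entries. This entry has its own objective, about Medicaid enrollees, and is not labeled as the Aim 3 estimate. Aim 3 and Hypothesis 3b in the combined document do not themselves repeat the CHC limit. This removes any charge of concealment. It does not explain why the CHC restriction was dropped, and no other entry in the section supplies the expenditure result that the SAP planned.

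Three stronger readings are tempting, and the documents do not support them.
- *The analysis covers all Oregon Medicaid adults.* It covers the 37% who remained after the exclusions.
- *It cannot answer the CHC question.* CHC patients with continuous coverage are probably inside the sample, and the protocol describes a link by Medicaid identifier. The file names do not show whether a CHC flag exists.
- *Most of the analyzed people never used a CHC.* The 58% applies to the starting frame, set against 121 study facilities, while another entry cites 184 Oregon CHCs. It says nothing firm about the 230,602.

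Two further objections stand. Nothing shows the expenditure analysis actually drawing the SAP's inference about care within CHCs, so that harm is potential. And CHC use after 2014 may itself result from gaining coverage. The SAP warns of this attribution bias where it discusses non-users in the post-period, so any CHC restriction must be defined before expansion.

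**Conclusion.** The mismatch is real, and the entry does not explain it. As described, the listed expenditure analysis estimates spending among continuously enrolled Oregon Medicaid adults statewide. It does not estimate the Aim 3 contrast among CHC patients, and it gives no basis for attributing spending changes to care within CHCs.

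At least 361,347 of the 622,513 people in the frame (58%) lie outside the Oregon study patients in Table 2. The CHC share of the final 230,602 cannot be derived, and neither can the direction or size of any difference in the result. The conclusion rests on what the entry states, assuming that it does not omit a CHC restriction that was in fact applied. The issue should be fixed; it does not invalidate the statewide result as a statewide result.

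**What to change.** 1. State in the expenditure entry that the population departs from the SAP and IRB protocol section 5d, and why.
2. Fit the same weighted two-part model in the linked Oregon CHC cohort, with the SAP's clinic fixed effects, and report it as the Aim 3 expenditure result. Alternatively, report a CHC stratum. Keep the statewide sample as secondary.
3. Define CHC membership, and the clinic assigned to each patient, from visits before 1 January 2014.
4. If the SAP's inference about care within CHCs is to be drawn, report CHC and external spending separately.
5. If the linked data are no longer accessible, limit the conclusion to continuously enrolled Oregon Medicaid adults and do not attribute spending changes to CHC care.

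**Cost.** Mainly analysis time, since Data Sources says that the linkage was done. The sample shrinks and intervals widen, by about 1.5 to 2.1 times under the assumptions in the working. Patients who first used a CHC after expansion are lost, so the result describes established patients.

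Access is not assured. The state research application says that OHSU, where the code is held, receives the data with OHP and OCHIN identifiers removed. Item 9 of the Information Access Agreement makes use valid for one year unless extended in writing, and requires return or destruction within 60 days of completion. Items 1 and 5 need no data.

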Objective	To examine rates of opioid prescribing, Opioid Use Disorder (OUD) prevalence, and OUD treatment among Oregon Medicaid enrollees after the ACA Medicaid expansion; and to understand how insurance history and dose type are related to OUD diagnosis rates, as well as whether patients with OUD in the expansion population (of new enrollees and those ‘returning’ after coverage gaps) had different MAT participation rates than those previously continuously enrolled.
Study Population	Adults aged 19+64; continuously insured by Oregon Medicaid 1/2014-12/31/2015. N=225,295.
Exclusion Criteria	Patients with coverage gaps during study period; dual eligibles; hospice care; cancer diagnosis other than non-melanoma skin cancer.
Independent Variables	
 1. Insurance group 2. Episode type
Dependent Variables	
 1. Opioid filled prescription 2. Documented diagnosis of OUD 3. Chronic opioid use 4. Receipt of medication assisted treatment
Covariates	Age, sex, race, urban/rural, co-morbidities, zip code, federal poverty level, employment, and number of episodes
Analysis Plan	
 1. Inverse propensity weighting 2. Absolute standardized mean difference 3. Prevalences 4. Logistic regression 5. Cox proportional hazard 6. Multinomial logistic regression
Data Set Name	OUTPAT, OUTPATIENT_2015Q4, RX , RX_Q42015, SAMPLE_FLAGGED_FOR_EXPORT

	hospice_providers, mat_codes, opioid_ndcs_2016
Code Location	Box at OHSU

Following uninsured patients through Medicaid Expansion: healthcare utilization and diagnosed conditions

Full Citation	[name], N., S. Valenzuela, M. Marino, H. Angier, B. Hatch, M. Hoopes and J. E. DeVoe. Following uninsured patients through Medicaid Expansion: healthcare utilization and diagnosed conditions. Submitted Ann Fam Med 11/18.
Objective	Assess healthcare utilization and diagnosed health conditions among a cohort of community health center patients who were uninsured pre-ACA and follow them 24 months post-Affordable Care Act (ACA).
Study Population	All non-pregnant patients without insurance pre-ACA, aged 19-64 during the study period, with ≥ 1 ambulatory visit pre-ACA from 300 primary care CHCs 'live' on their EHR system as of 1/1/2012 in 11 states. N=138,246.
Exclusion Criteria	Pregnant women, insurance coverage prior to ACA.
Independent Variables	1. Insurance group
Dependent Variables	1. Healthcare utilization 2. Health conditions

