Health insurance facilitates access to care and reduces unmet healthcare needs,¹⁻⁴ yet 47 million Americans had no coverage in 2012.⁵ The ACA, the largest healthcare-related legislation in the United States (US) since Medicare's establishment in 1966, was enacted with the goal of expanding coverage to all citizens and legal residents.⁶ The ACA increases opportunities to gain health insurance, including expansions in Medicaid coverage to individuals earning \leq 138% of the federal poverty level (FPL) and the establishment of health insurance marketplaces. In 2012, the Supreme Court ruled that states were not legally required to implement Medicaid

expansions, and those opting out could not be penalized.⁷ As of December 2014, 27 states (and D.C.) implemented the expansion;⁸ the number of states is increasing. Many persons directly affected by these expansions are seen at community health centers (CHCs), which comprise much of our nation's healthcare 'safety net' and serve a rapidly increasing number of patients;⁹ in 2012, 36% of CHC patients were uninsured.¹⁰ The effect of the ACA on health insurance coverage and access to health care services is unknown, thus it is imperative to assess its impact.

4) Study Design

Secondary data analysis.

We will use electronic health record (EHR) data from the Accelerating Data Value Across a National Community Health Center Network (ADVANCE) clinical data research network (CDRN) data warehouse and Oregon Medicaid administrative data.

The ADVANCE CDRN is a unique 'community laboratory' for research with underrepresented populations that includes patients receiving care in safety net clinics. The ADVANCE CDRN data warehouse includes *integrated* longitudinal outpatient EHR data from several organizations, including OCHIN, Health Choice Network, Fenway Health, and Legacy Health.

Oregon Medicaid administrative data will be linked to OCHIN Oregon clinics in the ADVANCE CDRN to assess the receipt of healthcare services outside the ADVANCE network clinics and all healthcare expenditures.

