Ethnicity	Hispanic/non-Hispanic
Household Income	Federal poverty level; overall income; % FPL
Language Preference	English, Spanish, other, etc.
Clinic Information	Rural/urban; panel size; panel demographics; provider characteristics
Medicaid Expansion Status	ACA Medicaid expansion state/non-expansion state; date of expansion
Visits	Frequency and type of visits
Healthcare Need	Special need because of a chronic condition
Insurance	Coverage status and type at visit; changes in status and type over time; % covered over time
Continuity of Care	% of visits at the same site and with same provider; Continuity of Care Index
Service Utilization	Number and types of all billed encounters overall and yearly; all services received; disease specific services received; preventive services received; amount of time services are delayed
Expenditures	Categories; overall
Health outcomes	Biomarkers such as HbA1c, blood pressure, body mass index, cholesterol measurements, etc
Diagnoses	Number and type of chronic and acute conditions
Community Vital Signs	Community markers of social determinants of health (e.g., fast food availability, parks, income distribution, racial/ethnic breakdown, healthy food availability, income distribution, homeownership)
Cancer registry elements	Date of diagnosis, primary type, stage, sequence, histology, behavior, grade, insurance at diagnosis, family history, treatment, vital status, date of death

9) Privacy, Confidentiality and Data Security

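### The Oregon expenditure analysis lists no income measure among the covariates for its propensity-weighted comparison, so residual income confounding may affect the between-group spending levels

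*Combined protocol and SAP*

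**What the plan says.** The expenditure entry describes itself as a "Retrospective cohort study using inverse-propensity weights to adjust for differences between groups". The independent variables are given as "Insurance group, time, and their interaction terms, mean monthly expenditures", and a separate two-part hurdle model is run for each type of spending. The Covariates row lists "age, sex, racial and ethnic background, rural setting, and comorbidity level as assessed by the enhanced Charlson comorbidity index score". It names no FPL, income or employment.

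The Exclusion Criteria of the same entry remove dual eligibles and patients "whose 2014-2015 eligibility did not depend on FPL (e.g. pregnant women"). Coverage must be continuous from January 2014 to December 2015, which leaves 230,602 of 622,513 adults.

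Three other places bear on this:

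- The IRB protocol, section 3 (Background), describes the policy as "expansions in Medicaid coverage to individuals earning" up to 138% of FPL.
- The opioid entry under Data Analyses covers Oregon Medicaid adults continuously insured over the same two years (N=225,295), distinguishes new, returning and continuous enrollees, and also uses inverse propensity weighting. Its covariates are "Age, sex, race, urban/rural, co-morbidities, zip code, federal poverty level, employment, and number of episodes".
- The IRB protocol, section 8 (Data Analysis), lists household income among the potential variables, as "Federal poverty level; overall income; % FPL".

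Neither document gives a reason for leaving FPL out of the expenditure analysis, or a sensitivity analysis for it.

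**The concern.** Expansion eligibility was set by income, so the chance of being newly rather than continuously insured in January 2014 is tied to income by policy. Income is also plausibly related to health and spending beyond what age, sex, race/ethnicity, rurality and a comorbidity score capture. A variable related to both group and outcome belongs in the propensity model unless there is a stated reason to leave it out.

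This design cannot remove a stable income difference in another way. The cohort starts in January 2014 and has no pre-period. The SAP (B.4.4, econometric analyses for Aim 3) itself notes that newly insured patients cost Medicaid nothing beforehand. No baseline spending can be subtracted, so the weights carry the whole adjustment of the level contrasts. Those contrasts bear on Hypothesis 3b, which concerns spending of the newly insured relative to the already insured.

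**Working it through.** **1. The plan's own figure.** 230,602 / 622,513 = 37.04%, which agrees with the stated 37%. It is the only figure in the entry that can be checked, and it does not bear on the bias.

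**2. The two Oregon entries side by side.**

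| | Expenditure entry | Opioid entry |
|---|---|---|
| Population | Oregon Medicaid, continuous 2014-2015 | Oregon Medicaid, continuous 2014-2015 |
| N | 230,602 | 225,295 |
| Groups | new, returning, continuous | new, returning, continuous |
| Weighting | inverse propensity | inverse propensity |
| Income covariates | none listed | FPL, employment |
| Claims files in common | OUTPAT, OUTPATIENT_2015Q4, RX, RX_Q42015 | the same four |

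**3. Size of the level bias.** The documents give neither FPL by insurance group nor the relation of income to spending. Every input in this step and the next is therefore an assumption, and the results are a range, not an estimate.

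*Continuous form.* Bias in the spending ratio = exp(d × s) − 1. Here d is the FPL difference between groups in SD units that remains after weighting, and s is the log-spending slope per SD.

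- d = 0.2, s = 0.05: exp(0.010) − 1 = 1.0%
- d = 0.5, s = 0.10: exp(0.050) − 1 = 5.1%
- d = 0.8, s = 0.15: exp(0.120) − 1 = 12.7%

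*Binary form.* Bias factor = [1 + p_new(R − 1)] / [1 + p_cont(R − 1)]. Here p is the lower-income share in each group, and R is the ratio of lower-income to higher-income spending given the listed covariates.

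- Equal shares, or R = 1: 1.00
- p_cont 0.80, p_new 0.70, R = 1.05: 1.035 / 1.040 = 0.995
- p_cont 0.80, p_new 0.50, R = 1.25: 1.125 / 1.200 = 0.938
- p_cont 0.80, p_new 0.50, R = 1.50: 1.250 / 1.400 = 0.893
- p_cont 0.95, p_new 0.50, R = 1.50: 1.250 / 1.475 = 0.847

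Taken together, the level bias runs from about 0-1% to 13-15%. The sign follows from the assumptions. If R were below 1, or the shares were reversed, the bias would go the other way.

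**4. Group-by-time ratio.** Group membership is fixed over 2014-2015. With p fixed and R constant, the same factor multiplies both periods and cancels, so the bias is 1.00 on the ratio scale. If R drifts, with shares 0.80 and 0.50:

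- R from 1.25 to 1.20: (1.100 / 1.160) / 0.9375 = 1.011
- R from 1.25 to 1.10: (1.050 / 1.080) / 0.9375 = 1.037

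**The case against.** Several counter-arguments have force.

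- **The weight model is not written out.** The entry has a one-line Covariates row and separately mentions weights. The Decision Log (05/09/16) places detailed documentation with each dataset. That the row is the propensity model is a fair inference, not a statement. It still names the adjustment set, and income is not in it.
- **The opioid entry is imperfect evidence.** One Covariates row serves several models there, so it does not prove that FPL is in that study's weights. The two entries also name different sample files. It shows that FPL was obtained for closely similar enrollees, not that it sits in the expenditure file.
- **Restriction is partial control.** Limiting the cohort to FPL-dependent eligibility narrows income. It does not equalise income within the remaining range.
- **The interest is in change over time.** A stable income effect cancels from the group-by-time ratio. This stands, and confines the point mainly to level contrasts.
- **Overlap may be poor.** If income helped determine who was covered before 2014, adding FPL could give unstable weights. That is a reason to examine overlap and report it.

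A reader might also infer four stronger things that the documents do not support:

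- *Income differences are in fact being read as insurance-group effects.* Neither the imbalance nor the income-spending relation is given.
- *The bias is as large as the reported uncertainty.* No uncertainty is reported. Assuming a coefficient of variation of 2 to 4 and 50,000 to 76,867 enrollees per group, 1.96 × CV × √(2/n) gives half-widths of 2.0% to 5.0%. That ignores the weighting and the two-part model, and the low-end bias of 1% is smaller than either half-width.
- *This is the only study without FPL.* The entries on visit disparities and pre-existing conditions list no covariates, the smoking cessation entry lists no FPL, and the Oregon Latino entry restricts to low income without listing it. In the long-term coverage entry FPL is a clinic-level distribution, and in the adolescent entry it is an exposure.
- *The analysis departs from the SAP.* The SAP refers to Box 6 for covariates, and Box 6 is not in the available text.

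**Conclusion.** The point holds as a possible source of residual confounding and a worthwhile improvement, not as a demonstrated bias. The listed adjustment set omits a variable that the policy ties to group membership, in a design with no pre-period to difference it out, and no justification is given. The exposure lies in the between-group spending levels. The group-by-time ratio is at risk only if the income effect changes over the two years (a factor of about 1.01 to 1.04 in the worked examples). The level bias could be negligible or as much as 13-15%. That range rests wholly on assumed imbalance and assumed income-spending relations, and its direction is unknown. The conclusion also rests on reading the Covariates row as the propensity model.

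**What to change.** 1. State the covariates of the propensity model explicitly.
2. Add FPL at January 2014 enrolment, and employment if it is on file.
3. Report standardized mean differences and overlap for FPL across the three groups, before and after weighting.
4. Where overlap is thin, trim to the common FPL range, or also enter FPL in both parts of the hurdle models. State how many enrollees are lost and how the target population changes.
5. Report the level contrasts and the group-by-time terms with and without FPL.

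If FPL cannot be used, say why, and give a sensitivity analysis for an unmeasured income difference in the form shown in the working.

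The cost is a refit of the weights and models. No new data collection appears necessary, provided FPL can be linked to the expenditure sample. The statistical price is more variable weights, some loss of precision and possibly a trimmed cohort.
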